Objectives	Primary objective Assess the rates of BSI from the use of 3CBs (e.g., SmofKabiven [®] , Kabiven [®] , others) compared to hospital compounded bags (HCBs) in patients requiring PN in Spanish hospitals
	 Secondary objectives Determine the extent of treatment requirement in patients receiving 3CBs compared to hospital compounded bags Assess mortality rate in patients receiving 3CB compared to patients receiving HCBs Evaluate the influence of additions made to the PN bags on BSI rates Assess the effect of manual versus automated compounding on BSI rates Evaluate the rate of PN-associated adverse events in patients receiving 3CBs compared to HCBs, including sepsis, organ failure, metabolic impairment, hepatic dysfunction and electrolyte imbalance Assess the achievement of the nutritional target in patients receiving 3CBs compared to HCBs
Investigational sites	Approximately 10 sites using 3CBs and/or HCBs
Study design	Retrospective observational data retrieval in a two-step design: In step 1, data from 30% of the target patient number will be obtained from the investigational sites to evaluate study feasibility and perform an interim analysis assessing statistical power.In step 2, the study will be continued by documenting further 70% of patients if the statistical power is > 60%.
Observational drug	Any PN administered in 3CBs, containing all three major macronutrients (glucose, amino acids, lipids)
Comparator	Hospital compounded PN bags containing all three major macronutrients
Patients	Adult hospitalized patients receiving PN in Spain, treated on any ward and by any medical discipline within the hospital (intensive care unit, normal ward; surgery, non-surgery)

Outcome parameters Primary outcome parameter

 BSI only with concomitant antimicrobial treatment (bacteria and/or candida), thereby excluding patients with contaminations

Secondary outcome parameters

- Rate of peripheral line associated BSI
- Rate of central line associated BSI
- Single organ failure, multiple organ failure
- Mortality
- PN-related adverse events of special interest: metabolic impairment (hyperglycemia, hypertriglyceridemia), hepatic dysfunction (cholestasis: transaminases, gamma-glutamyl transferase, alkaline phosphatase, bilirubin), electrolyte imbalance (sodium, potassium, chloride, calcium, phosphate, bicarbonate)
- Changes in prealbumin, C-reactive protein
- Achievement of caloric target (hypo-, hyperalimentation)

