- Extent of treatment requirement: Hospital length of stay, ICU length of stay, antibiotics, antimycotics, vasopressors and mechanical ventilation

These parameters will be documented for the multivariate analysis - if available - and the discussion. These are not outcome parameters:

- Demographic data: gender, age, weight (BMI)
- Admission type: elective, emergency, transferral
- Reason for hospital admission: leading diagnosis
- Reason for ICU admission: surgical, medical, trauma
- Primary disease
- Duration of hospitalization before venous catheter (VC) placement and PN
- Type of venous access: central, peripheral
- VC insertion and maintenance according to "Bacteremia Zero" protocol
- Type of hospital compounding: automated, manual
- VC related influence: number of VC; number of lumen of VC; site of VC placement (jugular, subclavian, femoral); insertion of VC in ER, OR, ICU; clinical experience of staff placing and handling VC and PN; duration of VC; duration of PN and duration between VC placement and PN; SOP for hygiene in place (cap, mask, sterile gloves sterile full body drape)
- Indication for PN
- Percentage of PN (supplemental PN, total PN)
- Omega-3 fatty acids and glutamine as active ingredients

- Additions of vitamins, trace elements and/or electrolytes to PN bag
- Addition to PN bag made under sterile conditions in the pharmacy, or on the ward
- Co-morbidities: cancer, malabsorption, pancreatitis, liver failure, renal failure, diabetes, malnutrition (SGA), gastrointestinal disorder
- Enteral, oral nutrition, oral nutritional supplements
- Antibiotic and antimycotic treatment (number, duration, antibiotic free days)
- Availability of a Nutrition Support Team at the center
- Hospital characteristics: region, teaching status, urban/ rural, number of beds
- APR-DRG severity of illness
- APACHE II score or SAPS II score

Inclusion criteria

General:

- Adult patients \geq 18 years
- Hospitalized between 1. January 2014 and 31. December 2015

Study-specific:

- PN for at least three consecutive days
- PN as 3CBs or hospital compounded, containing all three major macronutrients
- complete medical record regarding treatment information, PN administration details and, if applicable, adverse events

Exclusion criteria

General

Prior participation in this study

Study specific

- BSI at admission to the participating hospital (not hospitalacquired), i.e., prior to the 3rd calendar day of admission
 - where day of admission is calendar day 1

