	Final analysis: Baseline demographics, co-morbidities and hospitalization characteristics will be reported descriptively by means of standard deviations and medians with ranges for continuous variables and by counts and percentages for categorical variables. Incidence rates for BSI will be reported by treatment group. Multivariate logistic regression will be used to create a model to estimate the risk of BSI. The model will be adjusted for covariables as risk factors, potential confounders, baseline differences, etc. As variable-selection method correlations will be calculated for the rough selection and then backward elimination selection will be applied in the logistic regression model with a significance level of 10%. The risk of BSI will be reported as adjusted odds ratios with 95% confidence limits. For secondary/ further variables multivariate regression models will be used.
Observation period	Length of stay at the participating hospital
Planned start and end	Data retrieval for step 1: September 2016 – January 2017 Data retrieval for step 2: March – June 2017
Principal investigator	[name] PhD Madrid, Spain

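### The plan does not commit to a baseline term for the changes in prealbumin and C-reactive protein, which are compared between non-randomised bag groups

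*Combined protocol and SAP*

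**What the plan says.** All references are to the combined protocol and SAP.

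- **Study design**: "Retrospective observational data retrieval in a two-step design". Bag type is not randomised. Under Patients, any ward and discipline is eligible, including intensive care.
- **Outcome parameters, secondary**: "Changes in prealbumin, C-reactive protein". No baseline definition, follow-up time or scale is given.
- **The covariate list that follows the secondary outcomes** opens: "These parameters will be documented for the multivariate analysis - if available - and the discussion. These are not outcome parameters". It covers demographics, admission, catheter, PN, co-morbidity, hospital and severity items, among them "APACHE II score or SAPS II score". It contains no starting value of prealbumin or C-reactive protein.
- **Statistical analysis, Final analysis**, on the logistic model for bloodstream infection (BSI): "The model will be adjusted for covariables as risk factors, potential confounders, baseline differences, etc". A correlation screen and backward elimination at the 10% level are described for that model.
- **Same section**, for everything else: "For secondary/ further variables multivariate regression models will be used". No covariates are named.

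**The concern.** A change can be computed only if a starting value exists, so the baseline is at hand for every patient analysed. The plan does not say that it enters the model. Bag groups drawn from a mix of intensive-care and ward patients can plausibly start at different levels of two acute-phase markers.

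Two things are at stake. The first is precision, because a change score without a baseline covariate has more residual variance than a baseline-adjusted model unless the correlation is perfect. The second is interpretation. If both groups drift towards a common mean, the group that starts with higher C-reactive protein or lower prealbumin will appear to improve more with no bag effect at all. The severity scores and the malnutrition item on the list are partial proxies for the starting level, and they are collected only where available.

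**Working it through.** **1. What the text permits.** The covariate list is not closed and is confined to non-outcome parameters. The sentence on secondary models names no covariates. The mention of baseline differences belongs to the BSI model. Two analyses therefore comply equally: change regressed on bag type and listed covariates, and the same model with baseline added.

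**2. The plan's own figure.** The documents give no number for either marker. The only sample size is 1891 per group for BSI, at 10.8% against 13.8%. The two-sided pooled formula is

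n = [1.96·√(2·0.123·0.877) + 0.8416·√(0.108·0.892 + 0.138·0.862)]² / 0.03² = 1881.

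This is within 0.5% of 1891. I use 1891 below only as an upper limit for the number of paired values.

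**3. Assumptions, none from the documents.** Equal SDs (set to 1) in both groups and at both times; correlation ρ between baseline and follow-up; residual baseline difference d between groups; no true bag effect; two-sided 5% test. If other covariates are in the model, read ρ and d as what remains after them.

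**4. Formulas, if both groups regress to a common mean.**

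- Residual variance of change: 2(1 − ρ). With baseline adjustment: 1 − ρ². Share removed by adjustment: 1 − (1 + ρ)/2 = (1 − ρ)/2.
- Ratio of standard errors, change to adjusted: √(2/(1 + ρ)).
- Size of the difference carried into the change contrast: (1 − ρ)d.
- Rejection rate ≈ Φ(b/SE − 1.96) + Φ(−b/SE − 1.96), with b = (1 − ρ)d and SE = √(2(1 − ρ)·2/n).

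Results for d = 0.2 SD and n = 1891 pairs per group:

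| ρ | Variance, change | Variance, adjusted | Share removed | SE ratio | Carried over (SD) | Rejection, change |
|---|---|---|---|---|---|---|
| 0.3 | 1.40 | 0.91 | 35% | 1.24 | 0.14 | 95% |
| 0.5 | 1.00 | 0.75 | 25% | 1.15 | 0.10 | 87% |
| 0.7 | 0.60 | 0.51 | 15% | 1.08 | 0.06 | 66% |
| 0.8 | 0.40 | 0.36 | 10% | 1.05 | 0.04 | 49% |

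Example at ρ = 0.5: SE = √(1.00·2/1891) = 0.0325; 0.10/0.0325 = 3.07; Φ(3.07 − 1.96) = 0.87. Simulation with 500 runs gave 89% for change and 3.8% for the adjusted model at ρ = 0.5, and 69% and 5.4% at ρ = 0.7.

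**5. Sensitivity to d and to the number of pairs.** With d = 0.1 SD and 1891 pairs per group, rejection is 44%, 34%, 22% and 16% for ρ = 0.3, 0.5, 0.7 and 0.8. At ρ = 0.5 and d = 0.1 it falls to 12% with 500 pairs per group and 8% with 200. At ρ = 0.5 and d = 0.2 with 567 pairs (30% of 1891), it is 39%. The carried-over difference does not depend on the number of pairs.

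**6. The opposite case.** Suppose the groups differ by a stable d and each regresses to its own mean. The expected change is then equal in both groups, and the change score is unbiased. The adjusted model is off by (1 − ρ)d. At ρ = 0.5 and d = 0.2 this is 0.10 SD, with SE = √(0.75·2/1891) = 0.0282, so 0.10/0.0282 = 3.55 and rejection ≈ Φ(3.55 − 1.96) = 94%. Simulation with 1000 runs gave 3.6% for change and 93.9% for the adjusted model; at ρ = 0.7 it gave 5.2% and 71.5%.

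**The case against.** A reader might infer that the plan leaves baseline out of the model. The documents do not support that. The covariate list is expressly for parameters that are not outcomes, so two outcome markers would not be expected on it. The sentence on secondary models is silent rather than exclusionary, and the one adjustment approach that is described leans towards adjusting for baseline differences. This stands: the finding is a missing commitment, not a prescribed error. Carrying the BSI wording over to these models would not settle the matter, because the variable-selection rule would come with it and retention would not be guaranteed.

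The stronger objection is that the bias runs one way only under an assumption. In non-randomised groups the change score and the baseline-adjusted model answer different questions (Lord's paradox). Step 6 shows that adjustment can create the same size of error that it removes in step 4, and the documents do not say which situation applies. This also stands, and it is why the change-score comparison should be kept beside the adjusted one.

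Third, the rejection rates use assumed inputs and complete pairs. The inclusion criterion on complete records covers treatment, PN details and adverse events, not laboratory values, so pairs may be far fewer. The formulas also ignore the other covariates, which may shrink d. Finally, no listed objective names either marker. All of this limits the weight of the point. It does not remove the gap.

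**Conclusion.** The point holds as a gap in pre-specification for two secondary outcomes. The plan allows a change-score regression with no baseline term. Under the equal-SD assumption, adding the term removes 15% to 35% of residual variance for ρ between 0.7 and 0.3. Under the further assumption of a common mean, leaving it out passes 30% to 70% of any residual baseline difference into the bag contrast over the same range.

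Three stronger readings fail:

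- The whole baseline difference does not become a bag effect; only the fraction (1 − ρ) does, because the change already subtracts baseline.
- The high rejection rates are not properties of this study. They follow from a chosen ρ, d and number of pairs.
- Baseline adjustment is not a guaranteed cure for bias in non-randomised groups.

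The BSI hypothesis, its analysis and the sample size of 1891 per group are untouched. This is a small, nearly free improvement.

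**What to change.** In Statistical analysis, Final analysis, add wording such as: *Prealbumin and C-reactive protein will each be modelled with the last value before the first PN bag as a covariate that is always kept in the model, alongside the other adjustment covariates. The adjusted comparison of change scores will be reported as a sensitivity analysis. Because bag type is not randomised, the two methods rest on different assumptions; if they disagree, the result will be reported as inconclusive.*

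Add the two pre-PN values to the list of documented parameters. State the follow-up time, which either analysis needs before it can be run, and how missing pre-PN values are handled. A log scale for C-reactive protein is optional.

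The cost is a few sentences, two list entries and one additional model per marker. The baseline values are already needed to compute the changes. Patients without a pre-PN value drop out, as they already do for a change.

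### No care-setting or organ-support covariate is fixed at the first PN bag and kept in the BSI model, although ICU and ward patients are mixed

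*Combined protocol and SAP*

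**What the plan says.** The Patients section takes in adults "treated on any ward and by any medical discipline within the hospital (intensive care unit, normal ward; surgery, non-surgery".

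Under Outcome parameters, the last secondary outcome is "Extent of treatment requirement: Hospital length of stay, ICU length of stay, antibiotics, antimycotics, vasopressors and mechanical ventilation". No time point is attached to it, and the Observation period is the stay at the participating hospital, not the time from the first bag.

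A separate list follows, introduced by "These parameters will be documented for the multivariate analysis - if available - and the discussion. These are not outcome parameters". It includes "APACHE II score or SAPS II score", "APR-DRG severity of illness", "Reason for ICU admission: surgical, medical, trauma" and, among the catheter items, "insertion of VC in ER, OR, ICU". It has no item for ICU or ward location, ventilation or vasopressors when PN began.

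Under Statistical analysis, Final analysis, "The model will be adjusted for covariables as risk factors, potential confounders, baseline differences, etc". Candidates pass a rough selection by correlation and then backward elimination at a 10% level. No covariate is named as staying in the model regardless of its p-value.

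**The concern.** Bag type is not randomised here. Where the patient was treated, and whether organ support was running when PN began, could plausibly affect both the choice of bag and the risk of BSI. If so, the adjusted odds ratio is protected only if the model holds a measure of that state which is taken at or before PN start, exists for every patient and cannot be dropped. The plan does not guarantee any of the three.

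A second problem concerns the treatment-requirement objective. Ventilation or vasopressors begun before the first bag cannot have been caused by the bag, yet an outcome defined over the whole stay includes them. A group with more patients already on support at PN start would look worse on this outcome for that reason alone.

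**Working it through.** **1. The plan's own figure.** Inputs from Sample size: BSI 10.8% and 13.8% (mean 12.3%), significance level 0.05, power 0.80. Taking the test as two-sided (the plan does not say) with pooled variance:

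n = [1.960 × √(2 × 0.123 × 0.877) + 0.842 × √(0.108 × 0.892 + 0.138 × 0.862)]² / 0.03² = 1881 per group.

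The plan states 1891, which gives 80.2% power on the same method. The sample size reproduces within 0.5% and is not in dispute. It supplies the yardstick of 3 points.

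**2. What each listed item offers as a baseline adjuster.**

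| Item | Role in plan | Tied to patient's state at first bag? | Defined for every patient? | Kept in model? |
|---|---|---|---|---|
| APACHE II or SAPS II | candidate covariate | scoring time not stated | where available; no rule for combining the two scores or for patients with neither | can be eliminated |
| APR-DRG severity | candidate covariate | time not stated | where available | can be eliminated |
| Reason for ICU admission | candidate covariate | time not stated | no level for never in ICU | can be eliminated |
| Place of catheter insertion | candidate covariate | describes the catheter; interval from placement to PN is listed separately | no ward level | can be eliminated |
| ICU stay, vasopressors, ventilation | secondary outcome | whole stay | presumably | not listed as covariates |

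No row meets all three conditions.

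**3. Crude confounding, first set of assumptions.** With no true bag effect, the crude BSI difference equals (difference in ICU share between groups) × (ICU minus ward BSI risk). The documents give neither factor, so these are assumed values:

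- 10-point imbalance, 6-point gap: 0.10 × 0.06 = 0.6 points (20% of 3).
- 10-point imbalance, 12-point gap: 0.10 × 0.12 = 1.2 points (40% of 3).
- 15-point imbalance, 6 to 12 point gap: 0.9 to 1.8 points (30% to 60% of 3).

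**4. Crude confounding, second set.** Overall BSI is 12.3% as in the plan. The 40% ICU share and the ICU/ward risk ratios of 2 and 3 are assumed. Ward risk = 0.123 / (1 + 0.4 × (RR − 1)).

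- RR 2: ward 8.8%, ICU 17.6%, gap 8.8 points. Imbalances of 10, 20 and 30 points give 0.9, 1.8 and 2.6 points.
- RR 3: ward 6.8%, ICU 20.5%, gap 13.7 points. The same imbalances give 1.4, 2.7 and 4.1 points.

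**5. What this shows.** Steps 3 and 4 size the confounding in an unadjusted risk difference. The planned estimate is an adjusted odds ratio. How much remains after adjustment depends on how complete the severity scores are and when they were taken, which the documents do not say.

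**The case against.** The strongest reply is that the plan does adjust for acute severity. It names two acute severity scores and APR-DRG severity for the multivariate analysis, along with admission type, leading diagnosis, indication for PN and time in hospital before catheter and PN. ICU information also sits among the covariates, through reason for ICU admission and catheter insertion in the ICU. The covariate set is left open-ended. Being an outcome does not bar a variable from the model either: antibiotics and antimycotics appear in both lists.

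Most of this stands, and it rules out several readings that a reader might infer:

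- **That the main acute-severity confounder is left out.** The severity measures are listed as candidates.
- **That ventilation and vasopressors cannot be adjusted for.** They are collected. What is missing is their status at the first bag.
- **That reason for ICU admission is known to include transfers caused by a BSI.** The item is undated, so this is possible but not stated.
- **That 20% to 40% of the planned effect is the bias in the primary result.** Those figures are crude and rest on assumed inputs.

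It is also fair that the documents give no evidence that care setting drives bag choice. With about 10 sites using either or both bag types, the choice may partly follow the hospital. The direction of any bias is unknown.

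The reply does not close the gap in step 2. A severity score recorded after a BSI may already reflect it. In a mixed cohort, missing scores may follow care setting, and no missing-data rule is given. An open-ended covariate set does not help if sites are not asked to record status at PN start.

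**Conclusion.** The point holds in limited form. The plan has candidate severity covariates, but none is tied to the patient's state at PN start, assured for every patient and protected from elimination. Care setting and organ support at the first bag are not requested as covariates at all. Confounding by care setting can therefore remain in the adjusted odds ratio. Separately, the treatment-requirement outcome as written includes support that preceded the bag.

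The size is uncertain. Crude confounding of 0.6 to 1.2 points against a planned 3 follows from an assumed 10-point ICU imbalance and an assumed 6 to 12 point risk gap. The residual after severity adjustment is unknown and should be smaller where usable scores exist. This warrants a change to the plan but does not show that the primary result would be wrong.

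**What to change.** - **Data form:** record ICU or ward location, ventilation (yes/no) and vasopressors (yes/no) on the day of the first PN bag for every patient, with start dates.
- **BSI model:** keep these three terms as fixed baseline covariates, exempt from the correlation screen and backward elimination.
- **Severity scores:** use them for adjustment only if measured at or before PN start.
- **Treatment-requirement outcome:** count only ventilation and vasopressor support started after the first bag.

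The cost is a few extra dates abstracted from charts already under review. Inclusion already requires a complete record of treatment information, so the dates should be obtainable. The analysis text needs short additions on the retained terms, score timing and outcome definition. The secondary outcome becomes slightly narrower. Three more terms are affordable: at the planned rates, 3782 × 0.123 gives about 465 BSI patients at the final analysis. The stated sample size need not change.

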- Immunosuppression due to concomitanttherapy (e.g. immunosuppressive therapy due to transplantation, use of glucocorticoids)or disease (e.g. HIV, leukemia)
- persisting vascular access (port, shunts for dialysis) used during PN episode
- femoral venous placement of central venous line
- burns (irrespective of severity), extensive skin injuries (e.g., Lyell's disease)
- chemo-/ radiotherapy during hospital admission period or up to 3 months before hospital admission
- change of PN delivery method during study period, e.g., from compounding to 3CBs (change of dosing and/or frequency during the observational period is allowed)

Sample size	The sample size must allow the comparison of BSI rates associated with three chamber bags with those associated with hospital compounded bags. Due to the high variability among studies reported in the literature, a mean scenario is considered based on the incidence of BSI infections reported in Spain [Bonet 2005; Aguilella 2012], i.e., an overall incidence of BSI of 12.3% with a difference between the groups of 3% (± 1.5%). Samples size are estimated assuming incidence rates of BSI in MCB of 10.8% and 13.8% in hospital compounded PN, respectively. A sample of 1891 patients per PN type (3782 patients in total) is required taking into account a significance level of 0.05, the influence of the interim analysis on statistical power, and a statistical power of 0.80.
Statistical analysis	Interim analysis: The study is run in a 2 stage group sequential design with an interim analysis (IA) after acquiring 30% of the total sample size. This allows a premature discontinuation if BSI rates and their difference, i.e., the actual power of the study, are substantially lower than planned. The study will be terminated after the IA if the conditional power based on the IA results will be smaller than 60%.

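### Excluding every patient who changes PN delivery method makes inclusion depend on an event after PN start, deletes BSIs that preceded the change, and is liable to bias the 3CB–HCB comparison

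*Combined protocol and SAP*

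**What the plan says.** The study-specific exclusion criteria list "change of PN delivery method during study period, e.g., from compounding to 3CBs". The only stated exemption is that "change of dosing and/or frequency during the observational period is allowed". Nothing exempts a switch that follows a BSI.

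The observation period is "Length of stay at the participating hospital", and the primary outcome is BSI treated with antimicrobials. The only exclusion that refers to BSI is "BSI at admission to the participating hospital (not hospitalacquired), i.e., prior to the 3rd calendar day of admission", which is tied to the day of admission and not to PN start or to a switch.

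The final analysis is a logistic regression giving adjusted odds ratios. The documents do not assign switchers to a first PN type, limit the exclusion to switches before a BSI, count switchers by group, or plan a sensitivity analysis that keeps them. The term study period in the criterion is not defined.

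**The concern.** Whether a patient will switch is unknown when PN starts. In a retrospective study the whole stay is on record when eligibility is judged, so the criterion selects on the patient's future. Two routes link that future to the outcome:

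- A BSI may prompt the change of bag type. The patient then leaves the data set and takes the event along, although it arose on the first bag type.
- A longer stay or longer PN gives more opportunity both to switch and to acquire a BSI, even if neither causes the other.

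The regression sees only the patients who remain. Where the BSI itself prompted the switch, no covariate among them can restore the deleted case. At stake are the reported incidence in each group and, if the relation differs by bag type, the primary odds ratio. The decision after the 30% interim analysis is also exposed, because conditional power is computed from the same selected patients.

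**Working it through.** **Inputs from the documents (Sample size section).** "assuming incidence rates of BSI in MCB of 10.8% and 13.8% in hospital compounded PN"; I apply the MCB figure to 3CB. Overall incidence is 12.3%, alpha 0.05, power 0.80, with 1891 per group.

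**Inputs assumed.** Switch probability without BSI, sN = 5%. Switch probability with BSI, sB = 10%, 15% or 20%. The documents give no switching frequency, reason or timing.

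**1. The plan's own figure.** The two-sided pooled two-proportion formula, without continuity correction, is

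n = [1.96·√(2 × 0.123 × 0.877) + 0.8416·√(0.108 × 0.892 + 0.138 × 0.862)]² / 0.03² = 1881 per group.

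This is 0.5% below the stated 1891, and power at 1891 is 80.2%. The sample size is not in question here.

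**2. Incidence after the exclusion.** With true incidence p,

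p* = p(1−sB) / [p(1−sB) + (1−p)(1−sN)].

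Example, HCB with sB = 20%: 0.138 × 0.80 = 0.1104; 0.862 × 0.95 = 0.8189; p* = 0.1104 / 0.9293 = 11.9%.

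**3. Effect on the odds ratio.** The formula multiplies a group's odds by k = (1−sB)/(1−sN). The observed odds ratio is therefore the true one times k(3CB)/k(HCB). The planned odds ratio is (0.108/0.892)/(0.138/0.862) = 0.756.

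**4. BSI-related switching in one group only, none in the other.** Power is unadjusted, two-sided, at 1891 analysed per group.

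| Group with switching | sB | Incidence in that group | Gap (points) | OR | Power |
|---|---|---|---|---|---|
| None | – | – | 3.0 | 0.756 | 80% |
| HCB | 10% | 13.8% → 13.2% | 2.4 | 0.80 | 61% |
| HCB | 15% | 13.8% → 12.5% | 1.7 | 0.85 | 38% |
| HCB | 20% | 13.8% → 11.9% | 1.1 | 0.90 | 18% |
| 3CB | 10% | 10.8% → 10.3% | 3.5 | 0.72 | 91% |
| 3CB | 15% | 10.8% → 9.8% | 4.0 | 0.68 | 97% |
| 3CB | 20% | 10.8% → 9.3% | 4.5 | 0.64 | 99% |

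**5. No true difference (12.3% in both groups).** With sB = 20% and sN = 5% in one group only, that group shows 10.6%. The gap is a spurious 1.7 points, and the chance of p < 0.05 is about 39% instead of 5%.

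**6. Cases without bias in the odds ratio.**
- sB = sN: k = 1, and neither incidence nor odds ratio changes.
- The same sB and sN in both groups: the k factors cancel and the odds ratio stays at 0.756. Both incidences are still understated (at 20% and 5%, 9.3% against 11.9%).

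**The case against.** Excluding switchers gives groups with one exposure each, which is a legitimate aim. Nothing in the documents says that switching is common or that it follows BSI. With about 10 sites using 3CBs, HCBs or both, some may offer only one type, and switching there may be rare. If switching depends only on bag type and recorded covariates, the conditional odds ratio is not biased, and the plan lists PN duration, comorbidities and severity scores for adjustment, though only where available. All of this stands. It limits what can be claimed, but it does not justify the rule, because assignment by first PN type keeps exposure equally unmixed up to the switch.

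A reader might infer three stronger points that the documents do not support:

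- *That the rule does bias the result, in a known direction.* The documents contain nothing on the frequency, reasons or timing of switching. A difference in overall switch rates between bag types would not be enough; the relation between BSI and switching must differ.
- *That adjustment can never help.* That holds where the BSI itself prompts the switch. It does not hold where switching is explained by recorded covariates.
- *That other exclusions delete cases in the same way*, such as "chemo-/ radiotherapy during hospital admission period or up to 3 months before hospital admission" or immunosuppression through "use of glucocorticoids". The first covers the whole stay and the second has no time anchor, but nothing suggests that these treatments follow a BSI, or do so differently by bag type.

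**Conclusion.** The point holds as a risk of bias that the plan leaves open and could cheaply close. Inclusion depends on an event after PN start, and a BSI that precedes a switch is deleted with the patient. Study period could mean the PN episode, the hospital stay or 2014–2015, but a switch during the PN episode is caught under each reading.

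Under the assumed rates, incidence in the affected group moves by 0.5 to 1.9 points against a planned 3-point difference. The comparison can move either way: towards no difference if the relation is confined to HCB, away from it if confined to 3CB. These figures are illustrations. The true size could be zero, and the documents do not allow an estimate.

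**What to change.** - Replace the exclusion: assign each otherwise eligible patient to the PN type started first.
- For switchers, define the binary outcome as BSI with onset before the switch, and record PN duration up to the switch. Alternatively, use a time-to-event model censored at the switch; the planned logistic regression cannot itself censor.
- Report the number of switchers by PN type and by timing relative to BSI.
- Add two sensitivity analyses: (a) first PN type with BSI over the full stay; (b) the present set, excluding all switchers.
- Define study period wherever the criterion is kept, including for analysis (b).

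**Cost.** Changes to the protocol and analysis wording, and one more date to abstract. The inclusion criteria already require complete records of PN administration, so the date should be available. Some patients will have shortened follow-up. Stopping the count at the switch may itself be informative if switching relates to BSI risk, which is why analysis (a) is needed; (a) in turn attributes some time on the second bag type to the first, so the two should be read together.
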